Sample Size and Power Estimates. A provider group within the proposed study setting reported a 29.4% prevalence of GBS positive women among the 316 who gave birth in 2016. Therefore, we expect a 30% GBS prevalence in the placebo group compared to the probiotic group. To determine the effect size of the intervention, a sample of 80 women will be required to test the difference in proportions of GBS colonization and IAP between groups (hypotheses 1a and 1d). Hypotheses are unidirectional. With the sample size of 80 and setting alpha = 5%, one tailed test, 80% power estimate, and confounding variables (yogurt ingestion, vaginal cleansing practices, and sexual activity) accounting for multiple R-square = 0.1, we will be able to reject the null hypothesis for an effect size of Odds Ratio (OR) = 0.17 for the logistic regression to compare the proportion of GBS positives between groups. When comparing the colony counts (GBS and Lactobacillus) and GI symptoms (hypotheses 1b, 1c and 2), the same sample size = 80, power = 80%, alpha = 5%, one tailed test; we can reject the null hypothesis for a Cohen d = 0.56. This is a medium effect size, indicating that we can detect a difference between groups equivalent to 0.56 standard deviations. However, if the effect of the treatment is smaller we will be able to identify it, but not reject the null hypothesis of being equal to 0. This information is important for design of a full scale efficacy trial of the probiotic intervention. In our published preliminary study, 15 we found an overall dropout rate of 23%, but 30% in the probiotic group. For the proposed study, we chose a conservative 30% dropout rate to assure that the sample size can be fully achieved within the study timeline. Therefore, a total sample of 116 will be targeted for enrollment. Hypotheses 1b, 1c, and 2 will be tested by doing a multiple group comparison of the change in colony count for GBS and Lactobacillus, and the GI symptom inventory (M-SODA-9) scores [Section 2.3.1.8.e].

Recruitment. A sample of 116 women who meet the inclusion criteria, low-risk, healthy and pregnant, 26 ± 2 weeks gestation, 18 years of age, will be recruited from a population of central city maternity care recipients who see either certified nurse-midwives or physicians at the prenatal clinics of Aurora Sinai Medical Center (ASMC) in Milwaukee, Wisconsin. Approximately 200 new prenatal patients are seen monthly. **Inclusion and exclusion criteria are detailed in Table 1.**

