	Data Collection Form (SDCF; Appendix B).	weeks	weeks	post-	weeks	months
	See Appendixes A-G for data collection forms for all	baseline	prenatal	birth	post-	post-
	procedures.	visit	visit		birth	birth
	Procedures					
Qualitative GBS	Vaginal to rectal GBS swab. Collected at prenatal visit and	Not	X	Not		
Colonization (+ or -)	sends to hospital lab, results found in record	indicated		indicated		
Quantitative GBS Colony	Separate vaginal and rectal GBS swabs. Collected at	X	X			
Counts	prenatal visit and SC send to [name] lab					
Quantitative Lactobacillus	Separate vaginal and rectal Lactobacillus swabs. Collected	X	X			
Colony Counts	at prenatal visit and SC mailed to [name] lab					
Intervention Adherence	Vaginal and rectal swabs collected at prenatal visit		X			
	(presence of probiotic species verifies adherence)					
	2. MEMS™AARDEX™ wireless electronic cap counter ^{58,59}			Х		
	3. Final Pill Count			Х		
Maternal GI Symptoms	M-SODA-9 ^{65,66} GI symptom scale (completed by subject)	Х	Х	Х		
IAP	IAP doses based on qualitative GBS result; also SC			Х		
	records prenatal antibiotic exposures from medical record					
Demographics	Demographic characteristics Questionnaire	Χ				
Questionnaire for Women	Questionnaire on diet containing yogurt, sexual practices,	Χ	Х	X		
	vaginal cleaning practices (completed by study subject)					
Maternal-Infant Postbirth	SC interviews mother for maternal and infant health events	L	L	X		L
Health	and potential adverse events; documents			Х	TC	TC, HR
Adverse Events (AE)	Prenatal providers and SC solicit AE and document.		Х	Х	TC	TC, HR

Abbreviations: X = in-person study visit; TC = telephone call; HR = health record review.

- a. **Qualitative GBS Colonization.** Consistent with the CDC guidelines, between 35-37 weeks gestation (T2), the subject (or provider) will obtain a vaginal to rectal swab for GBS colonization to determine the need for IAP. [NOTE: In 2019, the guidelines changed and the prenatal GBS screens were collected at 36 weeks gestation.] The analysis of this swab will be done at the hospital laboratory and the result is reported as positive or negative for GBS. This swab will be done after the study swabs to prevent contamination of either site.
- b. **Quantitative GBS Colony Counts.** GBS colony counts, from separate vaginal and rectal swabs collected before the qualitative swabs, will be measured by [name] lab for this study, using CDC-recommended procedures to identify the number of GBS CFUs per swab (T1 & T2).

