 - c. Quantitative Lactobacillus Colony Counts. The swabs of vaginal and rectal sites will be analyzed to

identify the actual number of Lactobacilli in each area, counted as CFUs per swab (T1 &T2).

- d. Intervention Adherence Measures
- d.1. **PCR** and **16s** rRNA **Targeted Sequencing**. Vaginal and rectal swabs for PCR and 16s rRNA targeted sequencing will be collected (T2) by the participant or her provider and sent to [name] lab for analysis to detect the presence of the probiotic strains contained in the probiotic intervention group, verifying adherence.
- d.2. **MEMS Caps.** Each opening of the MEMS[™] AARDEX[™] wireless electronic cap counters^{58,59} will be recorded electronically with a software link to a study computer accessible to the SC and [name].
 - d.3. **Pill Counts.** The MEMS cap counts will be verified by the pill count when the bottle is returned.
- e. **Maternal GI Symptoms.** Because currently available GI quality of life scales focus on specific pathologies, we adapted the previously validated 7-item, non-pain symptom scale of the Severity of Dyspepsia Assessment (SODA)⁶⁵ (Cronbach's α = 0.9) to operationalize this variable. For use during pregnancy, the symptoms of "diarrhea" and "constipation" were added, resulting in a 9-item scale. Participants rate the severity of each symptom over the past week on a 6-point Likert scale, ranging from 0 = *no problem, not present* to 5 = *very severe problem, markedly influences daily activities and/or requires rest.* The score on the 9 items is summed to arrive at a GI symptom score ranging 0-45. Our **Ante-Partum Gastrointestinal Symptom Inventory (AP-GI-SA)** was validated in a pilot study with a sample of 45 healthy pregnant women. ⁶⁶ We found Cronbach's α = 0.84, test-retest reliability, stability, and content and face validity (T1, T2, and T3).
- f. IAP. If GBS-positive, the number and type of IAP doses will be recorded by SC on the **Summary Data Collection Form (SDCF).** Additional prenatal and intrapartum antibiotic exposures for participants and infants will be recorded on this form by the SC as potential cofounding variables.
 - g. Potentially cofounding variables
 - g.1. Participants will complete the brief **Demographic Questionnaire (DQ)** at T1 only.

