- g.2. Participants will complete the **Questionnaire for Women (Q4W)** at T1-T3 visits. To improve the reliability of subject recall, the Q4W asks for a report of the past week's ingestion of yogurt, vaginal cleansing practices, and sexual activity. The Q4W was used by the co-investigators in our preliminary study.¹⁸
- h. **Maternal-Infant Postpartum Health Events.** The SC will interview the participant for a history of postpartum health events for herself or the infant (T4 and T5) and document appropriately on two forms:
 - h.1. Maternal health events, recorded on Maternal Peripartal Health Check (MPHC).
 - h.2. Infant health events, recorded on Infant Health and Wellness Form (IHWF).
- i. **Adverse Events.** All providers and study personnel will solicit information about potential adverse events (AE) at each study visit (T2 through T5). Participants will be asked to report any suspected side effects or AE at any point in between study visits to their providers, who will then notify the PI, and follow the protocol established in the Human Subjects Section. AE will be recorded on **Q4W** (T2, T3), **MPHC and IHWF** (T4-T5). **Data Management.** Database and entry screens for this project will be developed using Epidata. To minimize errors, data will be double-entered and checked for invalid codes, values that are out of range, invalid dates, and skip patterns. All data will be verified against the original forms and imported to Epidata for analysis. **Descriptive Analyses.** Means, standard deviations or frequency distributions will be reported for all variables. We will test for differences in demographic characteristics of two groups (Florajen3 and placebo), including confounding variables such as sexual activity, vaginal hygiene practices, yogurt ingestion, and prenatal antibiotic use. Chi-square and independent *t* tests will be used to compare mode of birth, gestational age at birth, and birth weight and length, to assess equivalence of groups. Chi-square, Fischer's exact tests, and Wilcoxon methods will be used to test for difference among binary and categorical variables.

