Plan for Missing Data. To estimate the overall treatment effect for the entire sample, an "intention to treat" analysis will be conducted, using our above likelihood-based analysis method for repeated measures, including data on all subjects who were randomized to study groups, thus allowing us to use all available data, rather than delete participants with missing values from the analysis of treatment effects. ^{67,68} Pattern mixture modeling ⁶⁹ will be used to understand the effects of protocol compliance. Thus, treatment effectiveness during the full intended duration of the protocol can be compared with the effectiveness of treatments while participants are compliant with them. ⁷⁰

Binary Outcomes Analyses: Aim 1. Using an intention-to treat approach, subjects will not be dropped from any preliminary analysis due to varying degrees of adherence with their group-specific therapy. The main hypothesis, 1a, along with hypothesis 1d, assess differences in proportions, and will be analyzed using a generalized linear model (GLM).^{71,72} Those response variables that are dichotomous (binomial distribution) will be analyzed using the logit link to assess the proportional difference in GBS-colonized women (hypothesis 1a)

and the proportion of women requiring IAP (hypotheses 1d). GLM allows us to include confounding variables in the same model providing an effect size measure for the treatment and confounding variables, the odds ratio (OR), which has direct interpretation as the odds difference of testing GBS positive.

Continuous Outcomes Analyses: Aims 1 and 2. A secondary analysis of research aims 1 and 2 will be conducted using a Gaussian distribution-based multilevel generalized linear mixed model to assess group differences in GBS (hypothesis 1 b) and *Lactobacillus* (hypothesis 1c) colony count changes from 28 weeks to 35-37 weeks, ⁷³ with time points (T1-T2) nested within subjects. Group differences can be estimated for both initial time point and slope. The treatment is expected to show a meaningful difference to the slope of colony count change. Confounding variables will be included as time-invariant covariates. Parameters that appear to be meaningless will be excluded, using log-likelihood (deviance) model comparison with a direct interpretation as the colony count slope difference between groups, which can be transformed into a standardized difference (Cohen's *d*).

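### Baseline GBS carriage is measured at T1 but not named as a covariate for hypotheses 1a and 1d; prespecifying it is a cheap improvement, not the correction of an error

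*Combined protocol and SAP*

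**What the plan says.** Binary Outcomes Analyses: Aim 1 analyses 1a and 1d with a binomial GLM and logit link. On covariates it says "GLM allows us to include confounding variables in the same model providing an effect size measure for the treatment", and it names none. Covariates appear in four other places:

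- Sample Size and Power Estimates allows for "confounding variables (yogurt ingestion, vaginal cleansing practices, and sexual activity) accounting for multiple R-square = 0.1" and gives a detectable OR of 0.17 "for the logistic regression to compare the proportion of GBS positives between groups".
- Item f (IAP): "Additional prenatal and intrapartum antibiotic exposures for participants and infants will be recorded on this form by the SC as potential cofounding variables". Item g adds the demographic form and the questionnaire on the same three behaviours.
- Descriptive Analyses compares the arms on baseline characteristics, "including confounding variables such as sexual activity, vaginal hygiene practices, yogurt ingestion, and prenatal antibiotic use". The list is introduced as examples, so it is open.
- Continuous Outcomes Analyses (hypothesis 1b) models GBS counts at T1 and T2 and notes: "Group differences can be estimated for both initial time point and slope". This is the only model said to use the T1 GBS data.

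Separate vaginal and rectal swabs are cultured "to identify the number of GBS CFUs per swab (T1 & T2"). The 1a outcome is a different test. For the T2 vaginal-to-rectal swab, "The analysis of this swab will be done at the hospital laboratory and the result is reported as positive or negative for GBS", and Table 2 marks that swab as not indicated at T1. Randomization is simple, with 58 bottles per arm; no stratification is described.

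**The concern.** Baseline status on something close to the outcome is usually the first candidate for adjustment. Here it is collected for every woman, yet the plan names only behaviours, antibiotics and demographics. Nothing in the allocation balances T1 carriage. Table 1 excludes GBS bacteriuria in the current pregnancy but not a positive T1 swab.

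A T1 imbalance would show in the 1b model, while the main hypothesis has no stated way to deal with it. Three things are at stake: some power, protection in the minority of trials where carriage is clearly unequal, and the credibility of a covariate chosen after the imbalance has been seen.

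**Working it through.** **1. The plan's own figures.** Inputs from Sample Size and Power Estimates: 80 evaluable women, one-sided alpha 5%, power 80%, placebo prevalence 30%, OR 0.17.

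- Probiotic prevalence: odds 0.17 × 0.30/0.70 = 0.0729, so p = 0.0729/1.0729 = 6.8%.
- Wald formula: N = (1.645 + 0.842)² × [1/(0.5 × 0.30 × 0.70) + 1/(0.5 × 0.0679 × 0.9321)] / (ln 0.17)² = 81.
- Dividing by 1 - 0.1 for the R-square gives 90 by Wald, or 75 to 76 by pooled-variance formulas. Fisher's exact power at 80 is 81.5%. The stated 80 lies among these.
- Expected positives: 40 × 0.30 + 40 × 0.0679 = 14.7.

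**2. Chance imbalance at T1.** The documents give no T1 carriage; assume 30%. With 40 per arm, the exact binomial probability of a gap of at least 6 women (15 points) is 0.179 in either direction and 0.089 in a given direction. For carriage of 20% and 40% the two-sided figures are 0.123 and 0.209.

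**3. Carry-over to T2.** Let s be persistence, the probability that a placebo-arm T1 carrier is positive at T2 (assumed 50%, 70% or 85%). Holding placebo T2 prevalence at 30%, the probability for a T1 non-carrier is (0.30 - 0.30s)/0.70 = 0.214, 0.129 or 0.064. A 10-point T1 gap then shifts the T2 difference by 0.10 × (s - that value) = 2.9, 5.7 or 7.9 points.

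**4. Power at 30% vs 6.8%.** Simulation, 40 per arm, one-sided 5%. The 70%/90% assay has 70% sensitivity and 90% specificity for carriage. Rows 1 and 2 use 4,000 trials per cell (Monte Carlo SE about 0.55 points). Rows 3 to 6 use 1,000 (SE about 1 point).

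| Comparison | Assay | s = 50% | 70% | 85% |
|---|---|---|---|---|
| Firth, three behaviours, without → with T1 | perfect | 87.2 → 88.1 | 86.1 → 91.6 | 85.8 → 95.8 |
| same | 70%/90% | 86.5 → 86.5 | 85.3 → 86.5 | 85.7 → 88.8 |
| Ordinary logit, three behaviours → Firth, treatment and T1 only | perfect | -1 | +4 | +10 |
| same | 70%/90% | -1 | +1 | +3 |
| Ordinary logit, three behaviours → Firth, all five terms | perfect | -2 | +3 | +9 |
| same | 70%/90% | -3 | -1 | +1 |

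A separate set of 1,500 trials per cell for the last comparison gave about -1, +4, +8 (perfect) and -2, 0, +1 (70%/90%). Part of the ordinary logit's advantage is a slightly higher type I error (roughly 4.4-6.7% against 4.0-6.2%). In rows 1 and 2, type I error is 4.5-5.4% without T1 carriage and 4.1-5.4% with it. These power levels exceed the plan's 80%, so read the changes and not the levels.

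For 1d, if 90% of positives and 5% of negatives receive IAP (assumption), the Firth-to-Firth gains are 1, 4 and 7 points (perfect) or 0, 0 and 3 (70%/90%).

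**5. When a gap has occurred** (Firth with behaviours, without → with T1; s = 50%, 70%, 85%).

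- True gap of 15 vs 9 carriers favouring the probiotic, no treatment effect: false positives 10%, 16%, 19% → about 5% with a perfect assay, but 10%, 15%, 21% → 8%, 11%, 15% with the 70%/90% assay.
- Gap in the 70%/90% count result itself, 14 vs 8 of 40 (probability 8.5% in a given direction): 8%, 11%, 14% → 5%, 5%, 5%.
- True gap against the probiotic, design effect present: power 78%, 69%, 61% without T1; with it, 87%, 91%, 96% (perfect) or 81%, 79%, 76% (70%/90%).

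**6. Sparse events and the odds ratio.** Events per non-intercept parameter: 14.7/4 = 3.7 with treatment and the behaviours, 14.7/5 = 2.9 with T1 carriage added, 14.7/2 = 7.4 with treatment and T1 carriage only. The chance of no positives among 40 probiotic women is 0.9321⁴⁰ = 6%. In ordinary fits with the behaviours, adding a perfectly measured T1 carriage at 80% persistence raised the share of very large or separated estimates from 6-7% to 23%. The conditional OR matching a marginal 0.17 is about 0.15, 0.10 or 0.05 at s = 50%, 70% or 85%.

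**The case against.** The strongest reply is that nothing here is wrong. No passage promises baseline adjustment, and the randomized comparison is valid without it. The T1 count comes from a different laboratory and different swabs than the outcome, so the perfect-assay rows are an upper bound. Every gain rests on carriage, persistence and assay figures that the documents do not give. The remedy also replaces the plan's estimator, and with all five terms it can lose power against the written model. Finally, the trial is meant to supply an effect size for a larger one, and a conditional OR of 0.05 to 0.15 is harder to carry forward than a marginal 0.17. All of this stands, and it shapes the size and form of the recommendation. It does not remove the case for deciding on the covariate in advance.

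Three stronger readings are tempting and are not supported:

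- A reader might infer that baseline GBS is excluded from 1a and 1d, so that an imbalance would go unmodelled there. The Descriptive Analyses list is open, the Binary Outcomes section closes no list, and the appendices are not in the public text. Baseline GBS is unnamed, not ruled out.
- A reader might infer that the planned test is biased or has inflated error. Averaged over randomizations it keeps its level; the raised false-positive rates in step 5 are conditional on a gap in one direction.
- A reader might infer that adjustment must raise power. It can do nothing, or cost 1 to 3 points against the plan's own model.

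**Conclusion.** The point holds as an improvement worth making, with medium confidence. The plan collects a baseline measure close to the outcome and does not name it for its main hypothesis.

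The average power gain is uncertain. It is near zero at 50% persistence or with a count that tracks carriage poorly, and reaches about 10 points only at 85% persistence with a perfect assay. Those figures assume 30% T1 carriage. At 20% carriage the perfect-assay Firth-to-Firth gains are 0.4, 2.6 and 8.1 points. At 40% they are 1.1 and 6.9 for persistence of 50% and 70%; 85% is impossible there, since 0.40 × 0.85 exceeds 0.30.

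The firmer reasons to act are the protection in step 5, which is only partial against a true gap when the assay is imperfect, and having the covariate choice on record before unblinding.

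**What to change.** In Binary Outcomes Analyses: Aim 1, before unblinding:

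- Name T1 GBS carriage, defined as any GBS CFU on the vaginal or rectal T1 swab, as the first covariate in the 1a and 1d models.
- Place the three behaviours after it. Keep them only if the roughly 15 expected positives can support them, by a rule written down now and applied without regard to arm.
- Use a Firth-penalised fit, because sparse events make ordinary estimates unstable.
- Keep women with a missing T1 swab by imputing the single pooled-arm T1 proportion. With 10% missing, simulated power was 86%, 91% and 95% (perfect assay, behaviours included), with type I error 4.3-4.7%.
- Report the marginal difference in proportions beside the conditional OR, and say that the latter is not comparable with the 0.17 in the power statement.

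The cost is a few sentences in the SAP and no new data. The downsides are a possible loss of 1 to 3 points of power if T1 carriage predicts the T2 result poorly, few events per parameter if the behaviours stay, and an OR that lies further from 1.

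### The Gaussian model for colony counts (1b, 1c) fixes neither the scale, nor a value for undetected counts, nor the baseline constraint, so the GBS slope and its Cohen's d are under-defined

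*Combined protocol and SAP*

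**What the plan says.** All references are to the combined protocol and SAP.

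- **Outcome.** Under Quantitative GBS Colony Counts, GBS is measured "from separate vaginal and rectal swabs collected before the qualitative swabs" and expressed as CFU per swab at T1 and T2. Lactobacillus has the same unit and visits. Neither item gives a detection limit or a value for a negative swab.
- **Model.** Continuous Outcomes Analyses: Aims 1 and 2 opens with "A secondary analysis of research aims 1 and 2 will be conducted" and continues "using a Gaussian distribution-based multilevel generalized linear mixed model to assess group differences in GBS" and Lactobacillus change, with T1 and T2 nested within subject. The result is to be read directly as the "colony count slope difference between groups, which can be transformed into a standardized difference", namely Cohen's d. No transformation or link is named.
- **Baseline.** The same section says "Group differences can be estimated for both initial time point and slope", and then "Parameters that appear to be meaningless will be excluded" by deviance comparison.
- **Planning figures.** Sample Size and Power Estimates expects 30% GBS prevalence on placebo. It gives OR 0.17 as the detectable effect for colonisation and d = 0.56 for colony counts and GI symptoms together (N = 80, 80% power, one-tailed 5%). It says that effect sizes will inform a full-scale trial.
- **Elsewhere.** Plan for Missing Data deals with missing values, not undetected ones. The Wilcoxon methods under Descriptive Analyses are for binary and categorical variables.

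**The concern.** A Gaussian slope in CFU is a difference in arithmetic means. If about 28 of 40 placebo women have no or very few GBS organisms, that mean is set by about 12 carriers, and mostly by the heaviest of them. The estimate can then be imprecise and even point the wrong way, although its d is meant to help design the next trial. If a log scale is chosen later, the reported fold-change depends on the value given to undetected counts, so an unstated choice would move the result.

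The baseline term is a separate weakness. In a randomised trial the groups share the same expected T1 mean. Estimating a group difference there, and removing it only if it looks unimportant, costs precision and makes the estimator depend on the data.

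**Working it through.** **1. The plan's own figure.** With 40 per arm (80 analysed, 1:1 allocation) and one-sided 5%, the noncentral t with 78 df gives 79.9% power at d = 0.56, and a detectable d of 0.561. The figure reproduces. It is a generic two-group effect and fixes no scale.

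**2. Carriage implied by the plan.** Placebo: 0.30 × 40 = 12 carriers. OR 0.17 gives odds 0.17 × 0.30/0.70 = 0.0729, a proportion of 0.0729/1.0729 = 6.8%, or 2.7 of 40 on probiotic. Both inputs refer to clinical GBS status, not to the separate study swabs, so they serve only as an illustration.

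**3. Population d on raw T2 counts when only carriage changes.** With p1 = 0.30, p2 = 0.068 and CV the coefficient of variation of carriers' counts:

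d = (p1 − p2) / √{[p1(1+CV²) − p1² + p2(1+CV²) − p2²]/2}

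- CV 0: 0.232/√[(0.210 + 0.063)/2] = 0.63
- CV 1: 0.232/√[(0.510 + 0.131)/2] = 0.41
- CV 2: 0.25
- CV 3: 0.17

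This d reaches 0.56 only if CV is about 0.44 or less. If probiotic carriers' mean count is also halved, the values are 0.79, 0.51, 0.31 and 0.21, and the limit is CV 0.84. The documents give no CV.

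**4. Simulation.** Assumptions, none of them in the documents: carriers' median 10^4 CFU, 30% carriage at T1, T1–T2 correlation 0.6, 70% persistence of carriage, detection limit 100 CFU (half of it is 50), and log10 SD among carriers as shown. There are 40 per arm and the test is one-sided at 5%. With two visits and complete data, the change score matches the planned model with the baseline group term kept. The T1-adjusted test stands for that term dropped.

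(a) Carriage falls from 30% to 6.8%:

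| Log10 SD | 0.3 | 0.5 | 1.0 | 1.5 |
|---|---|---|---|---|
| Power, raw change | 54% | 33% | 14% | 6% |
| Power, raw adjusted for T1 | 77% | 59% | 25% | 15% |
| Power, log10 (undetected = 50), adjusted | 91% | 91% | 87% | 82% |
| Wrong sign, raw change | 5% | 13% | 28% | 32% |
| Wrong sign, raw adjusted | 1% | 5% | 12% | 16% |

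(b) Carriage unchanged, treated carriers' counts fall by 1 log10:

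| Log10 SD | 0.3 | 0.5 | 1.0 | 1.5 |
|---|---|---|---|---|
| Power, raw adjusted | 98% | 85% | 27% | 10% |
| Power, log10 (undetected = 50), adjusted | 56% | 56% | 42% | 29% |
| Power, log10(CFU+1), adjusted | 24% | 26% | 23% | 19% |

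A repeat run moved individual cells by up to about 3 percentage points.

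**5. Dominance by single values.** The largest T2 count holds a median 21%, 30%, 53% and 69% of the placebo total at the four SDs.

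**6. Baseline adjustment.** It raised power in every non-null scenario, on every scale. In (a) at SD 0.3, raw goes from 54% to 77% and log10(CFU+1) from 75% to 92%.

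**7. Assigned value.** Under a fall in carriage, setting undetected counts to 1, 50 or 100 turns the same data into adjusted fold-reductions of 7.3–8.5, 3.3–3.4 and 2.8–3.0.

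**8. Type I error.** Raw change 1.8–6.0%, raw adjusted 1.8–5.4%, log analyses 4.4–5.4%.

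**The case against.** The strongest reply is that the plan nowhere says raw CFU will be analysed, and that a log scale is not automatically better. Both parts stand. Raw CFU is the literal reading of a silent text, so the defect is an unstated scale, not a stated wrong one. Hypothesis 1b concerns a fall in counts, and when only counts fall, scenario (b) shows adjusted raw ahead of the log analysis at SD 0.3 and 0.5.

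A reader might infer that log10(CFU+1) is the natural remedy. It is not. The step from 0 to about 4 log units swamps a 1-log change among carriers, so that analysis largely re-tests carriage (1a). In (b) it has the wrong sign in 16–20% of trials.

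A reader might also infer that d = 0.56 is wrong, or that it holds on the log scale. The documents support neither. It is a detectable effect shared with GI symptoms, it is correctly computed, and it is tied to no scale. The plan also says that a smaller effect would be estimated without rejecting the null.

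Finally, the plan already permits dropping the baseline group term, and the worst wrong-sign rates belong to the change score. That is fair, but permission to drop a term after looking at fit is weaker than fixing the constraint in advance.

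**Conclusion.** The concern holds as a gap in specification with a conditional consequence. For 1b and 1c the scale, the value for undetected counts and the baseline constraint are not fixed. On raw CFU the GBS slope and its d can rest on a few large values, and the size of the problem depends on a spread among carriers that the plan does not give. The benefit of a log scale depends on that spread and on whether treatment changes carriage or counts. The benefit of baseline adjustment appeared in every non-null scenario.

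The limits are these. The analysis is labelled secondary, 1a is unaffected, and there is no material inflation of type I error. For Lactobacillus only the unstated scale is established, because the argument from a majority of zeros rests on GBS prevalence. The 30% comes from clinical status, and carriage on the separate vaginal and rectal swabs may differ. A claim that the trial cannot detect a GBS count effect would go beyond the documents. The point should be fixed, with medium confidence in its size.

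**What to change.** Before unblinding:

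1. In Continuous Outcomes Analyses, constrain the groups to a common T1 mean for 1b and 1c, or use T1 as a covariate. Do not leave the baseline group term to deviance-based selection.
2. Analyse log10 CFU per swab with one fixed value for undetected counts tied to the assay's detection limit (for example half the limit), not log10(CFU+1). Add a sensitivity analysis for that value.
3. For GBS, report the contrast among carriers separately, as a descriptive result, so that a change in counts can be told from a change in carriage.
4. In Sample Size and Power Estimates, say that d = 0.56 is a generic detectable effect on the chosen analysis scale and is not claimed for raw GBS counts.

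The cost is SAP wording, with no new data or visits. Effects will be read as fold-changes that depend on the assigned value. Power can be lower than on raw counts if carriers' counts vary little and only counts change. Any of these choices made after unblinding should be labelled post hoc.
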